8.1.10 Visit 9 (Day 5 evening)

Patients will return to the site approximately 12 hours after Day 5 morning dosing. The following activities will be performed:

- Cleaning of the treated area by the unblinded staff
- Review diary for rescue/concomitant medications;
- Rescue medicine drug accountability;
- Adverse Event assessment.

Patients will undergo the **ninth** topical treatment at the site weighed on a digital scale, then applied by an unblinded study staff at the site who is not responsible for adverse events, global assessments, pain and tenderness measurements. Patients will wear a blindfold during treatment so that the identity of the IMP is blinded. Patients will be instructed to return approximately 12 hours to the site for the **tenth and final** treatment based on their established nominal time.

If the patient decides to take rescue medication prior to the next treatment, the patient will be instructed to complete the Global Assessments prior to taking the rescue medication.

8.1.11 Visit 10 (Day 6 morning)

Patients will return to the site approximately 12 hours after Day 5 evening dosing. The following activities will be performed:

- Cleaning of the treated area by the unblinded staff
- Limited physical exam (injured extremity);
- Urine pregnancy test (female patients only);
- Review diary for rescue/concomitant medications;
- Rescue medicine drug accountability;
- Adverse Event assessment.

Patients will undergo the **tenth** topical treatment at the site weighed on a digital scale, then applied by an unblinded study staff at the site who is not responsible for adverse events, global assessments, pain and tenderness measurements. Patients will wear a blindfold during treatment so that the identity of the IMP is blinded. Patients will be instructed to return approximately 12 hours to the site based on their established nominal time for final assessments.

If the patient decides to take rescue medication prior to the next treatment, the patient will be instructed to complete the Global Assessments prior to taking the rescue medication.

8.1.12 Visit 11 (Day 6 evening, End of Study)

Patients will return to the site approximately 12 hours after Day 6 morning dosing. The following activities will be performed:

- Cleaning of the treated area by the unblinded staff
- Vital signs (blood pressure, heart rate, respiratory rate and body temperature after 5 minutes in a sitting position);
- Review diary for rescue/concomitant medications;
- Rescue medicine drug accountability;
- Adverse Event assessment;
- POM VAS;
- Algometry measurements;
- Global assessments for efficacy and tolerability;
- Sensory questions related to smell and touch;
- Return of diary and rescue medication.

No topical treatment is performed for this visit. Upon return of all study materials and completion of all study procedures, the patient will be discharged from the study.

8.2 Efficacy Assessments

8.2.1 Assessment of Pain on Movement

Pain on Movement will be assessed using a 100 mm visual analogue scale at baseline and at each subsequent study visit.

Place a line on the 'Scale' that best characterizes how your injured extremity feels when it's moved *now*.

No Pain | Severe Pain

8.2.2 Algometry

Algometry will be performed at baseline and at each study visit. Algometric measurements will be performed using a calibrated caliper with digital pressure recording). Increases in pressure during measurement will be kept constant at $10 \text{ N/cm}^2/\text{s}$. The site of measurement will be marked with a water resistant marker, and measurements will be repeated at the same site. The measurements will be performed in such a way that the patient and the investigator cannot read the actual pressure exerted (covered display). The device stores the last exerted pressure,

which is then recorded on the case report form. A tenderness reaction is defined as the pressure that, under the above conditions, produced a painful sensation.

Additional information related to the algometry procedures will be detailed in a separate document.

8.2.3 Global Assessments of Efficacy and Tolerability

At 24 hours, 48 hours, 72 hours and 120 hours post dose, the patient and the investigator will rate global assessment of the treatment efficacy using a 5-point Likert scale.

Global Efficacy

How would you rate the study medication you received as a pain-reliever?

- 0 = poor
- 1 = fair
- 2 = good
- 3 = very good
- 4 = excellent

At 24 hours, 48 hours, 72 hours and 120 hours post dose, the patient and the investigator will rate global assessment of tolerability (quality of life) using a 5-point Likert scale.

Global Tolerability

Considering all the ways this treatment has affected you since you started in the clinical trial, how well are you doing?

- 0 = poor
- 1 = fair
- 2 = good
- 3 = very good
- 4 = excellent

If the patient completes the Global Assessment not at the time of the scheduled clinic visit (or between visits), then the investigator will complete the Global Assessment at the next scheduled visit.

Planned time points for all efficacy assessments are provided in the SoA and Section [8.1](#).

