4.1.1.2 Treatment Phase

All treatment applications will be performed by an unblinded staff at the site. The unblinded staff will not be responsible for any pain or tenderness assessments. The correct location for application of the gel will be marked with a water-resistant pen to ensure the gel is applied at the same site for each application during the entire study. The topical investigational medicinal product (IMP) will be gently applied without any massaging.

At site visits on Days 1, 2, 3, 4 and 6, algometric and pain on movement (POM) VAS assessments will be performed. Compliance will be evaluated by the investigator/designee. The investigator and patient will give a global assessment of the treatment efficacy and local tolerability using a 5-point Likert scale.

Patients will use a patient diary to record adverse events, concomitant/rescue medication use on Days 1, 2, 3, 4, 5 and 6.

The algometry/tenderness will be measured such that the greater the algometry value (N/cm²), the greater the pressure required to produce the first tenderness reaction. Therefore, greater algometry values indicate less pain at the site of interest.

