5.2 Safety variables

Secondary efficacy variables are:

- Safety (percentage of subjects with at least one TEAE);
- Incidence of adverse events.

The following parameters are recorded to assess the safety of the study drug:

- Adverse events (AEs).
AEs will be documented at Visit 1 to Visit 11.
- Vital signs and body temperature.

	Trial Substance:	BAY H6689	Study No.:	21559
	Short Title:	Acute Soft Tissue of the Lower Extremities	Sponsor:	BAYER HEALTHCARE LLC.

Pulse rate (bpm) and blood pressure (BP_s, BP_d (mmHg) as well as body temperature will be documented at the Baseline Visit (Visit 1), Visit 7, and Final Visit (Visit 11)).

- General physical examination.

Physical examination will be performed at Visit 1 (randomization visit), Visit 2, Visit 4, Visit 6, Visit 8, and Visit 10, as well as when judged necessary by the Investigator.

A general physical examination will be performed at Visit 1 and include the injured extremity and assessments of the Dermatological, Cardiovascular, Respiratory, Gastrointestinal and Neurological systems.

A limited physical examination of the injured extremity will be performed at Visits 2, 4, 6, 8 and 10. Any issues will be described as adverse event.

Examination will include general condition, dermatologic, eyes, ears, nose, throat, neck, thyroid, heart, respiratory system, abdomen, kidneys, skeletal system, extremities, lymphatic system, CNS, neurological conditions and other (to be specified).

- Height and body weight.

Height in centimeters (cm, without shoes) and body weight (kg, in indoor clothing, but without shoes) will be measured at Visit 1. The corresponding Body Mass Index (BMI) will be calculated.

- Pregnancy and assessments of fertility.

Female participants of child-bearing potential will undergo urine pregnancy testing at Visit 1 (prior to first dose) and Visit 10 (prior to last dose).

- Global tolerability

Global tolerability will be assessed by the investigators and the patients according to the following numerical scale at Visits 3, 5, 7, and 11, respectively:

- 0: poor
- 1: fair
- 2: good
- 3: very good
- 4: excellent.

- Sensory questions

During the final visit of the study (Visit 11), patients will be asked two sensory questions related to the IMP they received.

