14.5 Safety

The assessment of safety will be based mainly on the frequency of AEs that are treatment-emergent in the Safety Population. Formal statistical tests will not be conducted for differences in safety parameters between treatment groups. Only descriptive analyses will be conducted.

The incidence of all treatment-emergent AEs will be after grouping by body system and preferred term. For each preferred term and summarized over each body system overall, the table will present the number of patients in each treatment group in whom the event occurred and the rate (%) of occurrence. The incidence of all suspected-drug-related AEs will be tabulated similarly. The incidence of all treatment-emergent AEs will also be tabulated by severity

	Trial Substance:	BAY H6689	Study No.:	21559
	Short Title:	Acute Soft Tissue of the Lower Extremities	Sponsor:	BAYER HEALTHCARE LLC.

categories and relationship to the IMP. Seriousness, severity, relationship to IMP duration and outcome will also be listed.

Safety will also be summarized with respect to vital signs as mean levels by visit and change from baseline. Abnormal observations on physical exams will be listed.

The ordinal outcome (global assessment of tolerability) will be analyzed by the Cochran-Mantel-Haenszel test of general association, stratified by center and also by subgroup (strain/sprain, contusion).

Furthermore, the ordinal outcome (sensory questions) will also be analyzed by the Cochran-Mantel-Haenszel test of general association, stratified by center and also by subgroup (strain/sprain, contusion).

Listings of individual data will be presented.

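### The global tolerability question mixes treatment benefit with tolerance of the gel, yet the SAP classes and tests it as a safety variable

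*Protocol*

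**What the plan says.** Protocol 8.2.3 has the patient and the investigator each give two global ratings at 24, 48, 72 and 120 hours. The efficacy item asks "How would you rate the study medication you received as a pain-reliever". The second item asks "Considering all the ways this treatment has affected you since you started in the clinical trial, how well are you doing". Only this second-person wording is printed, so the form put to the investigator has to be inferred.

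The documents describe the second item in three ways:

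- Protocol 4.1.1.2: "The investigator and patient will give a global assessment of the treatment efficacy and local tolerability using a 5-point Likert scale".
- Protocol 8.2.3, which sits under Efficacy Assessments: patient and investigator "will rate global assessment of tolerability (quality of life) using a 5-point Likert scale".
- SAP 5.2, among the parameters recorded to assess drug safety: "Global tolerability will be assessed by the investigators and the patients according to the following numerical scale". SAP 14.5 (Safety) adds: "The ordinal outcome (global assessment of tolerability) will be analyzed by the Cochran-Mantel-Haenszel test of general association", stratified by center and also by injury subgroup.

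SAP 14.5 also says that safety parameters will be described only and that treatment groups will not be formally compared on them. SAP 14.8 says that after withdrawal for lack of efficacy, later assessments take the worst value documented. It makes no exception for tolerability.

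**The concern.** A tolerability rating in a safety section should answer one question: did the gel cause unwanted effects? This item asks for something broader. Its stem covers every effect of treatment, wanted or unwanted, and its closing words invite a judgement of present condition. A patient with an itching application site and good pain relief can reasonably answer very good. A patient with no side effect and persisting pain can answer poor.

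The trial expects the active gels to relieve pain better than placebo. An efficacy difference could then appear in the safety section as a tolerability difference. Protocol 2.3.1 names application-site reactions as the main risk of the naproxen gel, and no other scaled item rates tolerance of the gel (the sensory questions cover scent and appearance). Protocol 2.1 says the data will guide development decisions, so a statement that the gel is better tolerated than placebo could carry weight.

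**Working it through.** **1. The wording against its labels.**

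| Place | What the item is said to be | Does the printed question fit? |
|---|---|---|
| Protocol 4.1.1.2 | Local tolerability | No. Neither skin nor application site is mentioned |
| Protocol 8.2.3 | Tolerability, glossed as quality of life | Partly. It is a broad status rating tied to treatment |
| SAP 5.2 and 14.5 | A safety variable, tested between arms | No. Benefit is inside the question |

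Pain relief already has its own question, so the second item is presumably meant to measure something else. Its wording does not keep pain relief out.

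**2. How far benefit can leak into the score.** The documents give no figure for this item, so there is nothing to reproduce. What follows is an illustration.

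Inputs from the documents:
- 2:2:1 allocation with 75 randomized, i.e. 30:30:15 (Protocol 1.1)
- three sites (Protocol 4.1)
- 5% level without multiplicity adjustment (SAP 14.7)
- standardized efficacy effect versus placebo, stated as over 1 for algometry and pain-on-movement AUC 0-72 (Protocol 9.2); d = 1.0 is used

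Assumptions:
- The 1 SD effect carries over to perceived recovery in both active arms.
- True tolerability is equal in all arms.
- A share w of the item's variance comes from recovery.
- Placebo answers split 5/15/30/30/20% over the five categories.
- The Cochran-Mantel-Haenszel (CMH) test is run across three arms and stratified by center only. The SAP does not say whether it is three-arm or pairwise.
- There are no dropouts.

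Model: item = √w × recovery + √(1−w) × tolerability. The arms therefore differ on the latent item by √w × d, which is 0.50 SD at w = 0.25 and 0.71 SD at w = 0.50.

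The expected score on the 0–4 scale is the sum of the probabilities of exceeding each of the four cut-points:
- Placebo: 0.95 + 0.80 + 0.50 + 0.20 = 2.45
- Active, w = 0.25: 0.984 + 0.910 + 0.691 + 0.366 = 2.95, a difference of 0.50
- Active, w = 0.50: 0.991 + 0.939 + 0.760 + 0.447 = 3.14, a difference of 0.69

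Simulation results (2,000 trials per setting):

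| Share w from recovery | CMH, three arms | Rank test, naproxen vs placebo | Mean difference (points) |
|---|---|---|---|
| 0 | 4% | 5% | 0.0 |
| 0.25 | 16% | 30% | 0.5 |
| 0.50 | 32% | 50% | 0.7 |
| 0.75 | 46% | 71% | 0.8 |
| 1 | 62% | 80% | 0.9 |

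With no between-arm recovery difference (d = 0), CMH rejection stays at 3–4% and the rank test at 4–5% for every w. The excess needs both a benefit of treatment and some leakage into the item.

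**3. Imputation.** If more placebo patients withdraw for lack of efficacy, the rule in SAP 14.8 lowers their tolerability scores for a reason unrelated to the gel. The direction is the same. It was not simulated and is not in the table.

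**The case against.** The strongest reply is that the item carries little of the safety case.

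- It does not appear in the objectives and endpoints table (Protocol 3).
- Protocol 8.3 does not list it among the safety assessments, and Protocol 9.4.5 measures safety by adverse events and vital signs.
- SAP 14.5 bases safety mainly on treatment-emergent adverse events.
- Adverse events are collected at every treatment-phase visit, and the injured limb is examined at Visits 2, 4, 6, 8 and 10.

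This stands. A reader might infer that a real skin problem would be hidden behind good recovery. The documents do not support that, because those other routes would show it.

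A reader might also infer that the item measures recovery instead of tolerability. That goes too far. The stem is tied to what the treatment did, unwanted effects included, and no data show how patients answer. Nor does natural healing bias the comparison by itself, since it occurs in all arms. Only a between-arm difference in recovery does.

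It is also tempting to size the effect with a naproxen–placebo t-test on 30 versus 15 patients. At correlations of 0.3, 0.5 and 0.7 between item and recovery, that gives 15%, 34% and 58%. This is not the planned test. Because w is the square of the correlation, 0.5 and 0.7 correspond to w of about 0.25 and 0.50, where the three-arm CMH test gives 16% and 32%. General association also has no direction, so a significant result does not itself say which gel is better tolerated.

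Finally, 8.2.3 openly describes a broad construct, so replacing the question is partly a choice of instrument. That is fair, but it does not justify reporting a broad construct as safety.

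**Conclusion.** The item does not isolate tolerance of the gel, its labels conflict, and the SAP contradicts itself by ruling out formal tests on safety parameters and then planning one. If the plan is followed as written, part of an efficacy difference can be reported as a tolerability difference.

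The three-arm CMH test would reject in about 16% of trials if a quarter of the item's variance reflects recovery and 32% if half does, against about 4% if none does. These figures rest on a 1 SD recovery benefit, equal true tolerability and assumed answer frequencies. The share itself is unknown.

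The consequence is confined to what may be claimed from this item. The trial's main safety conclusion, built on adverse events, is little affected.

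**What to change.** **In the SAP, before unblinding.** In 5.2 and 14.5, rename the item as a global status or quality-of-life rating, move it out of Safety, and state that it is interpreted exploratorily. Base tolerability conclusions on application-site treatment-emergent adverse events. This also removes the conflict within 14.5 as far as this item is concerned. State in 14.8 whether the lack-of-efficacy rule applies to it.

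**In the protocol.** Reconcile the descriptions in 4.1.1.2 and 8.2.3.

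**If data collection has not started,** the alternative is to reword the item so that it asks only about unwanted or application-site effects of the gel, and to delete the quality-of-life gloss. It could then stay under Safety, provided 14.5 is made consistent about testing.

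**Cost.** The SAP route is text only, with no added visits or procedures, but the trial gives up a scaled tolerability claim. The rewording route needs a small amendment to one CRF item, and the new wording would be untested.

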8.2.4 Sensory Questions

During the final visit of the study (Visit 11), patients will be asked two sensory questions related to the IMP they received.

What is your opinion of the scent of the product?

- Strongly liked
- Liked
- Neutral
- Didn't like
- Strongly disliked
- Did not notice a scent

How do you feel about the appearance of the product on your skin post application?

- There is no difference in the appearance of my skin
- Strongly like
- Like
- Neutral
- Dislike
- Strongly dislike

8.3 Safety Assessments

All safety assessments are detailed in Sections [8.3.1](#), [8.3.2](#) and [8.3.3](#). Planned visits for all safety assessments are provided in the SoA.

8.3.1 Physical Examinations

A general physical examination will include the injured extremity and assessments of the Dermatological, Cardiovascular, Respiratory, Gastrointestinal and Neurological systems at Screening (Visit 1). Height and weight will also be measured and recorded.

A limited physical examination of the injured extremity will be performed at Visits 2, 4, 6, 8 and 10. Changes related to the physical exam will be documented on the source documents and case report form.

8.3.2 Vital Signs

Blood pressure, heart rate, respiratory rate and body temperature (oral) will be assessed. Blood pressure and pulse measurements will be assessed with a completely automated device. Manual techniques will be used only if an automated device is not available.

Blood pressure and pulse measurements should be preceded by at least 5 minutes of rest in a sitting position for the participant in a quiet setting without distractions (e.g., television, cell phones).

Vital signs (to be taken before blood collection for laboratory tests) will consist of 1 pulse and 3 blood pressure measurements (3 consecutive blood pressure readings will be recorded at intervals of at least 1 minute). The average of the 3 blood pressure readings will be recorded.

8.3.3 Pregnancy Testing

Female participants of child bearing potential will undergo urine pregnancy testing at Visit 1 (prior to first dose) and Visit 10 (prior to last dose).

8.4 Adverse Events (AEs), Serious Adverse Events (SAEs) and Other Safety Reporting

The definitions of adverse events (AEs) and serious adverse events (SAEs) can be found in Section 10.3. The definition of unsolicited and solicited AEs can be found in Section 10.3.

AEs will be reported by the participant (or, when appropriate, by a caregiver, surrogate, or the participant's legally authorized representative).

The investigator and any qualified designees are responsible for detecting, documenting, and recording events that meet the definition of an AE or SAE and remain responsible for following up all AEs (see Section 7).

The method of recording, evaluating, and assessing causality of AEs and SAEs and the procedures for completing and transmitting SAE reports are provided in Section 10.3.

8.4.1 Time Period and Frequency for Collecting AE and SAE Information

All SAEs will be collected from the signing of the informed consent form (ICF)] at the time points specified in the SoA (Section 1.3).

All SAEs will be recorded and reported to the sponsor or designee immediately and under no circumstance should this exceed 24 hours of learning of the event, as indicated in Section 10.3. The investigator will submit any updated SAE data to Bayer Pharmacovigilance within 24 hours of it being available.

Investigators are not obligated to actively seek information on AEs or SAEs after conclusion of the study participation. However, if the investigator learns of any SAE, including a death, at any time after a participant has been discharged from the study, and he/she considers the event to be reasonably related to the study intervention or study participation, the investigator must promptly notify the sponsor.

8.4.2 Method of Detecting AEs and SAEs

Care will be taken not to introduce bias when detecting AEs and/or SAEs. Open-ended and non-leading verbal questioning of the participant is the preferred method to inquire about AE occurrences.

8.4.3 Follow-up of AEs and SAEs

After the initial AE/SAE report, the investigator is required to proactively follow each participant at subsequent visits/contacts. All SAEs will be followed until resolution, stabilization, the event is otherwise explained, or the participant is lost to follow-up (as defined in Section 7.3). Further information on follow-up procedures is provided in Section 10.3.

8.4.4 Regulatory Reporting Requirements for SAEs

Prompt notification by the investigator to the sponsor of an SAE is essential so that legal obligations and ethical responsibilities towards the safety of participants and the safety of a study intervention under clinical investigation are met.

The sponsor has a legal responsibility to notify both the local regulatory authority and other regulatory agencies about the safety of a study intervention under clinical investigation. The sponsor will comply with country-specific regulatory requirements relating to safety reporting to the regulatory authority, Institutional Review Boards (IRB)/Independent Ethics Committees (IEC), and investigators.

An investigator who receives an investigator safety report describing an SAE or other specific safety information (e.g., summary or listing of SAEs) from the sponsor will review and then file it along with the Investigator's Brochure and will notify the IRB/IEC, if appropriate according to local requirements.

For all studies except those using medical devices, investigator safety reports must be prepared for suspected unexpected serious adverse reactions (SUSAR) according to local regulatory requirements and sponsor policy and forwarded to investigators as necessary.

